8.4 DROPOUTS & MISSING DATA

Number of missing values will be summarized and reported as appropriate.

8.5 WITHDRAWALS AND DEVIATIONS

All withdrawn subjects will be listed individually, including at least subject number, date and reason for withdrawal, and last visit performed.

Subjects with deviations will be listed individually, including subject number and observed deviation. Depending on the seriousness of the deviation, subject might be excluded from the population analyzed.

8.7 MEASURES TO MINIMIZE BIAS

8.7.1 ENROLLMENT/ RANDOMIZATION/ MASKING PROCEDURES

To avoid bias, the subjects will be randomized to receive the treatment on one side. All evaluators will be blinded as to which side received the active intervention. The blinded evaluators will observe the subjects, but both the evaluator and subjects will be told that no discussions are to take place between the two and that the subjects are to remain silent during the evaluator examination.

To ensure only the clinical investigator performing the procedures and the study coordinator know the assignment, each subject will have an envelope assigned to them to be held by the study coordinator with the subject's name on the outside and the assignment on the inside. Only after the laser treatment does the study coordinator allow the clinical investigator to see the inside of the envelope with the randomized group assignment.

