Non-ablative fractionated Thulium laser (Sciton Moxi) will be performed on level 3 and an Intense Hydration Mask will be applied to one side of the face with nothing on the other side for 30 minutes. After photos and evaluation, a hydration serum will be applied to both sides and patients will be sent home with masks to be worn at least 2 hours every day until deemed fully healed by the investigator
 - 2nd Arm (n=5)
Ablative full Erbium:Yag laser (Sciton Contour) will be performed at 200 microns and an Intense Hydration Mask will be applied to one side of the face with nothing on the other side for 30 minutes. After photos and evaluation, Vaseline will be applied on both sides of the face and the patient will be sent home with masks to be worn at least 2 hours every day until deemed fully healed by the investigator
 - 3rd Arm (n=5)
Microneedling with RF (Cutera Secret) will be done with a non-insulated needle at a depth of 200 and an Intense Hydration Mask will be applied to one side of the face with nothing on the other side for 30 minutes. After photos and evaluation, a hydrating serum will be applied on both sides of the face and the patient will be sent home with masks to be worn at least 2 hours every day until deemed fully healed by the investigator

All Arms

- Post-procedure pictures and questionnaires to be completed by subjects 30 minutes after the procedure
- Safety analysis and erythema scale to be performed by blind evaluators and a compliance analysis performed by study coordinator

Day 1-7 Follow-up assessments

- Daily in office follow-up assessments of study endpoints and safety until primary investigator deems patients healed from the procedure

1st Arm (n=5) Non-ablative fractionated Thulium laser (Sciton Moxi)

Post-procedure pictures and questionnaires to be completed by subjects for 3-7 days as determined daily by the primary investigator

2nd Arm (n=5) Ablative full Erbium:Yag laser (Sciton Contour)

Post-procedure pictures and questionnaires to be completed by subjects daily for 3-7 days as determined daily by the primary investigator

3rd Arm (n=5) Microneedling with RF (Cutera Secret)

Post-procedure pictures and questionnaires to be completed by subjects daily for 3-7 days as determined daily by the primary investigator

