3.2.2 SECONDARY ENDPOINTS

- The difference in the number of adverse events between the two sides of the face
- The difference in pain scores on each side of their face as rated by subjects
- The difference in patient satisfaction scores when rating the procedure on the left and right side of their face
- The difference in erythema on the left and right side of subject's faces as graded by blinded evaluators doing live assessments 30 minutes after the procedure
- The difference in healing time in daily photographs as rated by blinded evaluators

These endpoints will show if the Velez Intense Hydration face mask decreases skin temperature after a cosmetic procedure, if subjects are happy with the use of the mask, and if they provide significant reduction in pain, erythema, and healing time.

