5.1.4 PREPARATION

The subject's face will be cleansed with a cleansing cloth to remove all topicals such as make-up, sunscreen, and moisturizers. A topical numbing cream will be applied for 30 minutes and then removed before the subject's face will be cleansed with alcohol immediately prior to the laser procedure.

The product will be removed from original packaging, cut in half with a sterile scissor, and placed on the subject's assigned side within 5 minutes of the end of the procedure.

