5.1.7 DURATION OF THERAPY

The subject will remain in the office for 30 minutes with the Velez face mask applied immediately after their laser treatment.

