6.3 Photography

Photographs will be taken 30 minutes after application of the intense hydration mask. Photographs may also be taken to document AEs at the treating investigator's discretion. Site personnel will be thoroughly trained in the photographic equipment and techniques before study start. A Photography Standard Operating Procedure will be provided in a separate user guide.

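### The Day 0 clocks differ by up to 5 minutes, and no stated measure hides a just-uncovered cheek from the blinded evaluator

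*Combined protocol and SAP*

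**What the plan says.** **Application and wear.** Section 5.1.4 has the half mask "placed on the subject's assigned side within 5 minutes of the end of the procedure". For each of the three arms, the Schematic of Study Design says that "an Intense Hydration Mask will be applied to one side of the face with nothing on the other side for 30 minutes". Section 5.1.7 agrees on the length: "The subject will remain in the office for 30 minutes with the Velez face mask applied immediately after their laser treatment".

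**Assessment times.** Section 3.2.2 and the Protocol Summary define the erythema endpoint "as graded by blinded evaluators doing live assessments 30 minutes after the procedure". Section 3.1 also times the standard and thermal images from the laser procedure. The photography section (6.3) uses the other reference point: "Photographs will be taken 30 minutes after application of the intense hydration mask". The Précis in the Protocol Summary likewise counts the standard and thermal images from mask application.

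**Order of events.** The schematic and Section 6.2.2 place photographs and evaluation before serum or Vaseline goes on both sides. No section states when the Day 0 mask is removed, who removes it, or where the evaluator is at that moment.

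**Blinding.** Section 8.7.1 states: "All evaluators will be blinded as to which side received the active intervention". Three measures support this. The assignment is kept in an envelope held by the coordinator. Only the treating investigator and the coordinator know it. Evaluator and subject may not talk, and the subject stays silent during the examination.

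**The concern.** Two times are counted from different starting points, and the plan does not say which one governs. If the mask goes on after any delay, a site cannot give the full wear period and also have the evaluator grade at the stated time.

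The larger matter is what the evaluator sees. The comparator is bare skin with no sham. At grading, one cheek has just been under a hydrating mask and the other has been exposed throughout. If the first looks moist or carries an edge mark, the evaluator knows the side, whatever the envelope and the silence rule achieve.

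Erythema grading is a judgement, and Section 8.2 lists it for hypothesis testing. The Schedule of Events shows the blinded evaluator's examination on Day 0 only, so a compromised live grading cannot be repeated. Section 3.1 has the same evaluator grade edema and side effects, and Section 6.2.2 records adverse events that the evaluator observes. The between-side difference in adverse events is itself a secondary endpoint.

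The primary endpoint is affected in a narrower way. The thermal image needs one reference point and a fixed interval after uncovering, or the time since removal can differ between subjects.

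**Working it through.** The plan gives no figure of its own to reproduce here. The check is timing arithmetic, followed by a comparison of the blinding measures with what each one controls.

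**Inputs**
- Delay from end of procedure to mask application: *d* = 0 to 5 minutes (Section 5.1.4).
- Wear time: 30 minutes (Schematic of Study Design; Section 5.1.7).
- Live grading due: 30 minutes after the procedure (Protocol Summary; Section 3.2.2).
- Imaging due: 30 minutes after the procedure (Section 3.1), or 30 minutes after application (Précis; Section 6.3, photography).

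**Formulas**, with all clock times counted from the end of the procedure
- Mask off = *d* + 30.
- Overlap with grading = (*d* + 30) − 30 = *d*.
- Wear time if the mask is instead taken off at 30 minutes to permit grading = 30 − *d*.
- Gap between the two imaging clocks = (*d* + 30) − 30 = *d*.

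**Results**

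| Delay *d* (min) | Mask off (min) | Overlap with grading (min) | Wear if removed at 30 (min) |
|---|---|---|---|
| 0 | 30 | 0 | 30 |
| 1 | 31 | 1 | 29 |
| 2.5 | 32.5 | 2.5 | 27.5 |
| 5 | 35 | 5 | 25 |

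Only at *d* = 0 do the rules fit together. For any longer delay, either the grading is late by *d* or the wear is short by *d*, by at most 5 minutes.

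**Blinding measures in Section 8.7.1**
- Envelope: controls who can read the assignment. It does not affect what is visible on the face.
- Knowledge limited to the treating investigator and the coordinator: also controls access, not appearance.
- No discussion, and a silent subject: controls spoken disclosure, not appearance.

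None of the three deals with a cheek uncovered moments earlier beside one that was never covered. The coordinator's check in Section 6.1.1 covers photographs and paperwork only.

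**The case against.** The strongest reply is that the plan, read as a sequence, already works. The Précis and Section 5.1.7 have the mask applied immediately, so 5 minutes is an upper limit and not a schedule. The schematic describes 30 minutes of wear, then photographs and evaluation, then topical care on both sides. Redness under a mask cannot be graded, and topical care needs the mask off, so removal is implied. This stands. A reader might infer from the arithmetic that evaluators would be grading a masked cheek; the documents do not support that.

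A reader might also infer that silence is the only safeguard, or that erythema is the only thing the evaluator grades on Day 0. Neither is right. Section 8.7.1 also has the envelope and the restriction on who knows the side, and Section 3.1 adds edema and side effects.

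Nor do the documents show that the primary endpoint is read through the mask or is unblinded. No section tells staff to image with the mask on, and the Section 3.1 timing is a wording conflict with the Précis and the photography section.

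Finally, Section 6.3 refers to a separate photography procedure that is not part of the documents, and some protocol text was not available. Image timing or mask handling might be covered there.

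What the reply leaves standing is that removal is implied but not written, the grading clock disagrees with the implied order, and removal alone does not make the two cheeks look alike.

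**Conclusion.** The point holds as a minor one. The conflict between the clocks is certain from the text and amounts to 0 to 5 minutes per subject. It is zero only when the mask goes on at the moment the procedure ends.

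The threat to blinding is plausible but unmeasured. It rests on the assumption that moisture or an imprint can reveal the side. If that always happens, all 15 live gradings are unblinded; if it never happens, none are. Nothing in the documents narrows that range. The exposure is limited to the evaluator's live Day 0 grading of erythema, edema and side effects. For the thermal primary endpoint the finding is only that one reference point and a recorded interval are needed.

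**What to change.** 1. Reconcile the Protocol Summary (Précis and endpoint list), Section 3.1, Section 3.2.2 and the photography section to a single Day 0 clock: 30 minutes after mask application, with the mask then removed. Write removal down as a step and name the role that does it.
2. Take the thermal image first, at a fixed and recorded interval after removal, so that later handling of the skin cannot alter the temperature reading.
3. Next, have the unblinded staff already present handle both cheeks identically. The method is for the investigator to choose.
4. Admit the evaluator only after that, and say so in Section 8.7.1.

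The evaluator could also record a guess of the masked side, but this is optional and should not be read as a test of blinding. If the mask reduces redness, the less red cheek will tend to be guessed correctly without any leak, and 15 guesses would give an imprecise proportion.

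The cost is a few minutes' delay at the Day 0 visit and a protocol amendment, which needs IRB approval under Section 9.2 because the stated timing of the erythema endpoint and of the imaging changes. No extra subjects, visits or staff are needed.

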9.1 ETHICAL STANDARD

The investigator will ensure that this study is conducted in full conformity with Regulations for the Protection of Human Subjects of Research codified in 45 CFR Part 46, 21 CFR Part 50, 21 CFR Part 56, and the ICH E6.

9.2 INSTITUTIONAL REVIEW BOARD

The protocol, informed consent forms, recruitment materials, and all participant materials will be submitted to the IRB for review and approval. Approval of both the protocol and the consent form must be obtained before any participant is enrolled. Any amendment to the protocol will require review and approval by the IRB before the changes are implemented to the study. All changes to the consent form will be IRB approved; a determination will be made regarding whether previously consented participants need to be re-consented.

9.3 INFORMED CONSENT PROCESS

Informed consent is required for all participants. In obtaining and documenting informed consent, the investigator will comply with applicable regulatory requirements and should adhere to 45 CFR Part 46, 21 CFR Part 50, 21 CFR Part 56, and ICH GCP. Prior to the written informed consent, the consent forms will be provided to the participants. Consent forms describing in detail the study agent, study procedures, and risks will be given to the participant and written documentation of informed consent is required prior to starting intervention/administering study product.

The investigator will explain the research study to the participant and answer any questions that may arise. All participants will receive a verbal explanation in terms suited to their comprehension of the purposes, procedures, and potential risks of the study and of their rights as research participants. Participants will have the opportunity to carefully review the written consent form and ask questions prior to signing. The participants will have the opportunity to think about being a participant prior to agreeing to sign. The participant will sign the informed consent document prior to any procedures being done specifically for the study. The participants may withdraw consent at any time throughout the course of the trial. A copy of the informed consent document will be given to the participants for their records. The rights and welfare of the participants will be protected by emphasizing to them that the quality of their medical care will not be adversely affected if they decline to participate in this study.

9.4 PARTICIPANT AND DATA CONFIDENTIALITY

Participant confidentiality is strictly held in trust by the participating investigators, their staff, and the sponsor(s) and their agents. Therefore, the study protocol, documentation, data, and all other information generated will be held in strict confidence. No information concerning the study or the data will be released to any unauthorized third party without prior written approval of the sponsor.

The study monitor, other authorized representatives of the sponsor, representatives of the IRB or pharmaceutical company supplying study product may inspect all documents and records required to be maintained by the investigator, including but not limited to, medical records for the participants in this study. The clinical study site will permit access to such records.

The study participant's contact information will be securely stored at each clinical site for internal use during the study. At the end of the study, all records will continue to be kept in a secure location for as long a period as dictated by local IRB and Institutional regulations.

Study participant research data, which is for purposes of statistical analysis and scientific reporting, will be transmitted to and stored at the Siperstein Dermatology Group Boynton research office. This will not include the participant's contact or identifying information. Rather, individual participants and their research data will be identified by a unique study identification number. The study data entry and study management systems used by clinical sites and by Siperstein Dermatology Group research staff will be secured and password protected. At the end of the study, all study databases will be de-identified and archived at the Siperstein Dermatology's Boynton Beach research office.

9.4.1 RESEARCH USE OF STORED HUMAN DATA

Pictures and data collected under this protocol may be used in future publications. Access to stored pictures and data will be stored using codes assigned by the investigators. Data will be kept in password protected computers. Only investigators will have access to the samples and data.

10 DATA HANDLING AND RECORD KEEPING

10.1 DATA COLLECTION AND MANAGEMENT RESPONSIBILITIES

Data collection is the responsibility of the clinical trial staff at the site under the supervision of the site PI. The investigator is responsible for ensuring the accuracy, completeness, legibility, and timeliness of the data reported.

All source documents should be completed in a neat, legible manner to ensure accurate interpretation of data. Black ink is required to ensure clarity of reproduced copies. When making changes or corrections, cross out the original entry with a single line, and initial and date the change.

Clinical data (including AEs, concomitant medications, and expected adverse reactions data) will be entered into a 21 CFR Part 11-compliant data capture system. The data system includes password protection and internal quality checks, such as automatic range checks, to identify data that appear inconsistent, incomplete, or inaccurate. Clinical data will be entered directly from the source documents.

10.2 STUDY RECORDS RETENTION

Study documents will be retained for a minimum of 2 years after the formal discontinuation of the clinical study. These documents will be retained for a longer period, however, if required by local regulations. No records will be destroyed without the written consent of the sponsor, if applicable. It is the responsibility of the sponsor to inform the investigator when these documents no longer need to be retained.

10.3 PROTOCOL DEVIATIONS

A protocol deviation is any noncompliance with the clinical trial protocol. The noncompliance may be either on the part of the participant, the investigator, or the study site staff. As a result of deviations, corrective actions are to be developed by the site and implemented promptly. It is the responsibility of the site to use continuous vigilance to identify and report deviations within 7 working days of identification of the protocol deviation, or within 7 working days of the scheduled protocol-required activity. All deviations must be addressed in study source documents, reported to the IRB and sponsor. The site PI/study staff is responsible for knowing and adhering to their IRB requirements.

10.4 PUBLICATION

The PI will be responsible for submitting the data to a peer-reviewed journal within 6 months of the end of the trial.

11 CONFLICT OF INTEREST POLICY

The independence of this study from any actual or perceived influence, such as by the pharmaceutical industry, is critical. Therefore, any actual conflict of interest of persons who have a role in the design, conduct, analysis, publication, or any aspect of this trial will be disclosed and managed. Furthermore, persons who have a perceived conflict of interest will be required to have such conflicts managed in a way that is appropriate to their participation in the trial.
